2.4 Rationale for dosing and schedule

The planned schedule of a preoperative dose of nivolumab, flat dose 480 mg, given once 28 days prior to surgery (with an additional 14 day window). The rationale for flat dosing is noted below. The duration of preoperative treatment of approximately 28 days was initially chosen as a short time period is unlikely to allow significant progression of disease which might preclude complete surgical resection. However, a 14 day window is allowable (as needed for scheduling purposes, or if clinically appropriate for patients with clinical benefit/improvement, if deemed safe by the treating physicians (surgeon & medical oncologist). Furthermore if clinically indicated patients may undergo surgery earlier (see Section 4.1.2 regarding early surgery, salvage treatment).

Waiting 28-42 days after dosing before surgery would still allow for time to appreciate immune mediated cellular changes.

Flat (standardized) dosing of nivolumab as a single agent:

Nivolumab monotherapy has been extensively studied in a number of tumor types including NSCLC, MEL, RCC, and CRC with body weight normalized dosing (mg/kg). Nivolumab pharmacokinetics (PK) and exposures of subjects in these studies have been characterized by population pharmacokinetic (PPK) analysis of data collected in these studies, together with PK data from several phase 1, 2, and 3 clinical studies of nivolumab monotherapy in solid tumors. Population PK (PPK) analyses have shown

that the PK of nivolumab are linear, with dose proportional exposures over a dose range of 0.1 mg/kg to 10 mg/kg, and are similar across tumor types. Nivolumab clearance and volume of distribution were found to increase with increasing body weight, but the increase was less than proportional, indicating that a mg/kg dose represents an over-adjustment for the effect of body weight on nivolumab PK. Given the relationship between nivolumab PK and body weight, a flat dose is expected to lead to lower exposures in heavier patients, relative to the exposures in lighter patients.

Using the PPK model, nivolumab steady-state trough, peak and time-averaged concentration (Cminss, Cmaxss, and Cavgss, respectively) were predicted for a flat nivolumab dose of 240 mg Q2W and compared to those following administration of 3 mg/kg Q2W in NSCLC subjects. A dose of 240 mg nivolumab is identical to a dose of 3 mg/kg for subjects weighing 80 kg, which is the approximate median body weight of NSCLC subjects in the 3 Phase 2 and 3 BMS clinical studies of nivolumab monotherapy. The geometric mean values of Cminss, Cmaxss, and Cavgss with flat dosing are slightly (< 15%) higher than that produced by a 3 mg/kg dose, and the coefficient of variation (cv%) in these measures of exposure are only slightly (< 10%) greater than that of 3 mg/kg dosing.

Across the various tumor types in the BMS clinical program, nivolumab has been shown to be safe and well tolerated up to a dose level of 10 mg/kg, and the relationship between nivolumab exposure produced by 3 mg/kg and efficacy has been found to be relatively flat. Taken together, the PK, safety, and efficacy data indicate that the safety and efficacy profile of 240 mg nivolumab will be similar to that of 3 mg/kg nivolumab. Receptor occupancy studies now support a dose of 480mg IV every 4 weeks, which is thought to be equivalent to the 240mg IV every 2 week schedule. This flat dose maintains saturation receptor occupancy for greater than 4 weeks. Thus a single flat dose of 480 mg given 4 weeks prior to resection is recommended.

3. PATIENT SELECTION

3.1 Eligibility Criteria

Cohort 1: Subjects must have histologically confirmed previously untreated squamous cell carcinoma of the head and neck that is amenable to surgical resection as part of standard of care.

Cohort 2: Subjects must have histologically confirmed recurrent squamous cell carcinoma of head and neck, that is amenable for salvage surgery. Sites of recurrence may either be locoregional and/or distant. Distant metastatic disease is permissible in this cohort and can be addressed at an interval with systemic therapy (e.g. chemotherapy, targeted therapies), or local therapies (e.g. radiation, metastatectomy) as clinically indicated.

Distribution between both patient cohorts is aimed to be 1:1 but may vary.

For both cohorts:

- 3.1.1 The primary site should be a head and neck squamous cell carcinoma (including, but not limited to oral cavity, oropharynx, hypopharynx, or larynx, paranasal sinuses, nasal cavity). Squamous cell carcinoma of unknown primary, diagnosed in lymph nodes in neck, can be included but should be tested for p16 and confirmed with an HPV specific assay (testing NOT required for enrollment; can be done at an interval).
- 3.1.2 Subjects with oropharyngeal primary tumors must have confirmation of HPV tumor status per clinical standards, although not necessary at enrollment.
- 3.1.3 Subjects must have been determined to be candidates for surgical resection by a multidisciplinary team including a surgeon, a medical oncologist and a radiation oncologist.
- 3.1.4 Subjects must have at least one lesion that can be (or has been) biopsied at baseline.
- 3.1.5 Eastern Cooperative Oncology Group (ECOG) performance status 0 to 1 (see [Appendix A](#) for definitions).
- 3.1.6 Age ≥ 18 years.
- 3.1.7 Life expectancy of greater than 6 months.
- 3.1.8 Patients must have normal organ and marrow function as defined below:

| | |
|--|---|
| leukocytes | $\geq 1,500/\text{mcL}$ |
| absolute neutrophil count | $\geq 1,000/\text{mcL}$ |
| platelets | $\geq 100,000/\text{mcL}$ |
| total bilirubin | $\leq 1.5 \times$ institutional upper limit of normal (except subjects with Gilbert syndrome, who can have total bilirubin $< 3.0 \text{ mg/dL}$) |
| AST(SGOT)/ALT(SGPT) | $\leq 3 \times$ institutional upper limit of normal |
| Creatinine OR creatinine clearance | within normal institutional limits OR $\geq 40 \text{ mL/min}$ (using modified Cockcroft-Gault formula) for patients with creatinine levels above institutional normal. |

- 3.1.9 The effects of nivolumab on the developing human fetus are unknown.
 - 1) Women of childbearing potential (WOCBP) must have a negative urine or

serum pregnancy test (minimum sensitivity 25 IU/L or equivalent units of HCG) within 24 hours prior to the start of study treatment.

- 2) Women must not be breastfeeding
- 3) Women of childbearing potential (WOCBP) must agree to follow instructions for method(s) of contraception for the duration of treatment with study treatment and for 5 months post-treatment completion. Women should use an adequate method(s) of contraception (Refer to nivolumab IB for WOCBP and methods of contraception to be provided).
- 4) Males who are sexually active with WOCBP must agree to follow instructions for method(s) of contraception for the duration of treatment with study treatment(s) and 7 months post-treatment completion. In addition, male participants must be willing to refrain from sperm donation during this time. Men who are sexually active with WOCBP must agree to follow instructions for method(s) of contraception.

3.1.10 Patient understands the study regimen,

its requirements, risks and discomforts and is able and willing to sign the informed consent form. Voluntary signed and dated IRB/IEC approved written informed consent form in accordance with regulatory and institutional guidelines must be obtained before the performance of any protocol related procedures that are not part of normal patient care. Subjects must be competent to report AEs, understand the drug dosing schedule and use of medications to control AEs.

3.1.11 Measurable disease – either radiologically (per RECIST V 1.1) or clinically measurable on exam in order to assess treatment response.

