4.2.2 Determination of Eligibility

After eligibility is established, the study staff will register participants. The following are required to be submitted for successful registration:

- Copy of subject consent
- Copies of the following documents:
 - Diagnostic pathology reports (with HPV status for oropharyngeal SCC)

- Pathology report(s) from initial diagnosis
- Pathology report(s) from the recurrence
- Baseline cross-sectional imaging (as clinically indicated, report sufficient for enrollment)
- Laboratory reports including:
 - Complete blood count (CBC) with differential (including absolute lymphocyte count) and direct platelet count.
 - Chemistry: Albumin, SGOT (AST), SGPT (ALT), Bilirubin, Calcium, Creatinine, Glucose, Total protein, Urea nitrogen, Electrolytes (including sodium, potassium, chloride and bicarbonate).
 - Baseline thyroid function assay: Thyroid Stimulating Hormone (TSH). Abnormal endocrine results should be followed up per standard of care, and may require an endocrine consult and additional testing.
- Medical records documenting treatment history of the initial therapy for SCCHN before recurrence
- Other documents, if requested.

Study treatment cannot begin until the patient is registered and assigned to a treatment cohort.

Subjects who sign a consent form but do not initiate protocol treatment for any reason (e.g., subjects who are screen failures), and patients who do not undergo surgical resection will be replaced and will not count towards our accrual goal of 26 patients (Patient allocation ideally should be 1:1 between both cohorts but may vary). All patients who receive a dose of nivolumab will be evaluable for safety and feasibility.

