4.2.3 Pre-treatment criteria

Enrolled patients will need to meet the following criteria before receiving nivolumab.

| | |
|--|--|
| leukocytes | ≥ 1,500/mcL |
| absolute neutrophil count | ≥ 1,000/mcL |
| platelets | ≥ 100,000/mcL |
| total bilirubin | ≤ 1.5 X institutional upper limit of normal (except subjects with Gilbert syndrome, who can have total bilirubin < 3.0 mg/dL) |
| AST(SGOT)/ALT(SGPT) | ≤ 3 X institutional upper limit of normal |
| Creatinine OR creatinine clearance | within normal institutional limits OR ≥ 40 mL/min (using modified Cockcroft-Gault formula) for patients with creatinine levels above institutional normal. |

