4.10 Study calendar

| Procedure | Screening (Days -42 to -29) ^a | Day -28 | Pre- surgical evaluation (Days -7 to -1)** | Day 0 Surgery (up to day +14) | Post- surgical evaluation (Days 21 to 42) | Follow-up visits (Every 3-4 months for 1 yr; then every 6 months for 2nd yr.) ^{\$\$} | At the time of recurrence | Survival Follow-up (every 12 months) |
|--|--|------------|--|---|---|---|---------------------------------|---|
| Clinical Assessments | | | | | | | | |
| Physical Exam | X | X | X | | X | X | X | |
| Vital Signs | X | X | X | | X | X | X | |
| Performance status (ECOG) | X | X | X | | X | X | X | |
| Concomitant medicines | X | X | X | | X | X | X | |
| Toxicity assessments | X | X | X | | X | X | X | |
| Electrocardiogram (EKG) | X | | | | | | | |
| Laboratory Tests | | | | | | | | |
| CBC with diff | X | X**** | X | | X | X | X | |
| Chemistry including LFT | X | X**** | X | | X | X | X | |
| # IF abnormal LFTs draw: Hepatitis B/C serology | (X) [#] | | | | | | | |
| TSH | X | | | | X | X | | |
| Free T4 and T3 | X | | | | | | X | |
| PT/INR and PTT | X | | X | | | | X | |
| Pregnancy Tests (WOCBP only) | X | | X | | X | | X | |
| Treatment | | | | | | | | |
| Nivolumab | | X | | | | | | |
| CT neck/chest with IV contrast* | X | | X | | | (X) | (X) | |
| MRI neck with IV contrast, optional† | (X) | | (X) | | | (X) | (X) | |

| Procedure | Screening (Days -42 to -29) | Day -28 | Pre- surgical evaluation (Days -7 to -1) | Day 0 (and up to day +14) Surgery | Post- surgical evaluation (Days 21 to 42) | Follow-up visits (Every 3- 4 months for 1 yr; then every 6 months for 2nd yr.) ^{§§} | At the time of recurrence | Survival Follow-up (every 12 months) |
|---|-----------------------------------|----------------|--|---|---|---|---------------------------------|---|
| Correlative Blood/Tissue/Stool Studies | | | | | | | | |
| PBMCs, Serum, plasma (Blood collection 100 cc's) | | X ^b | | X | X | X | X | |
| Tumor biopsy/sample | X | | | X (resection specimen) | | | X | |
| Stool Sample | | X ^c | X | | X | X | X | |
| Oral Rinse ^d | | X | | | X | X ^d | X | |
| Medical & Dietary Questionnaire | | X | | | X | X | X | |
| Survival | | | | | | | | X |

- a. screening labs are permitted to be used for treatment if completed within three (+3) days of day -28
- b. Research blood permitted to be collected anytime after consent and prior to Nivolumab infusion (Days -42 to day -28)

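### The study calendar schedules no pregnancy test at dosing and lets older screening labs stand, although Section 3.1.9 requires a negative test within 24 hours before nivolumab

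*Combined protocol and SAP*

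**What the plan says.** Section 3.1.9, after noting that nivolumab's effects on the fetus are unknown, requires women of childbearing potential to have a negative urine or serum test, of a stated minimum sensitivity, "within 24 hours prior to the start of study treatment".

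The calendar in Section 4.10 lists the test under its laboratory heading, with this row: "Pregnancy Tests (WOCBP only) | X | | X | | X | | X". Read against the column headers, the marks fall at Screening, the pre-surgical evaluation, the post-surgical evaluation and recurrence. The Screening column covers Days -42 to -29. The Day -28 column, where nivolumab is given, is empty for this row. The blood count and chemistry rows do have a Day -28 mark.

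Footnote a is attached to the Screening column header: "screening labs are permitted to be used for treatment if completed within three (+3) days of day -28". It makes no exception for any laboratory test.

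Section 4.2.3 opens with "Enrolled patients will need to meet the following criteria before receiving nivolumab", and its table contains only haematology, liver and renal limits. The list of registration documents in Section 4.2.2 does not name a pregnancy test either.

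**The concern.** The eligibility rule and the schedule that should deliver it do not match. Study staff commonly work from the calendar and the pre-dose criteria. Here the calendar places the test up to two weeks before dosing, footnote a appears to accept a result two or three days old, and the pre-dose list is silent. A woman dosed on such a result would be in breach of 3.1.9 although the calendar had been followed.

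The stake is fetal exposure to a drug whose fetal effects the protocol calls unknown. There is one dose. Section 2.4 says it keeps receptors saturated for more than four weeks, and permanent discontinuation, the drug measure in Section 6.6, cannot undo a completed infusion. The next scheduled test is on Days -7 to -1, which is 21 to 27 days after dosing.

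**Working it through.** The plan gives no figure to reproduce. The check compares time windows.

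**Inputs**

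- Limit: 24 hours from test to dose (3.1.9).
- Dose day: Day -28 (4.10). Sections 4.1.1 and 4.3 say approximately Day -28; exactly Day -28 is assumed here.
- Only scheduled pre-dose test: Screening, Days -42 to -29 (4.10).
- Reuse of screening labs: within three days of Day -28 (footnote a). This is taken to mean up to three days before dosing. The (+3) in the footnote is ambiguous, but a result obtained after dosing could not support the dose.

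**Is the blank cell real?** The pregnancy row has all eight visit cells and lines up with the physical examination, blood count, TSH and PT/INR rows. The empty Day -28 cell is therefore not a table-extraction fault.

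**Gap from test to dose.** If the test is *d* calendar days before dosing, and both can occur at any hour, the gap lies between 24(*d* - 1) and 24(*d* + 1) hours.

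| Test day | *d* | Possible gap | Meets 24 hours? |
|---|---|---|---|
| -29 | 1 | more than 0, up to 48 h | only if timed within 24 h of infusion |
| -30 | 2 | more than 24, up to 72 h | never |
| -31 | 3 | more than 48, up to 96 h | never |
| -42 to -32 | 4 to 14 | more than 72 h | never |

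**Counts**

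- Screening days: 42 - 29 + 1 = 14.
- Screening days that always fail, Days -42 to -30: 42 - 30 + 1 = 13.
- Screening days usable under footnote a, Days -31 to -29: 31 - 29 + 1 = 3. Two of these, Days -31 and -30, always fail.

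**Does another provision restore the limit?** The baseline work-up in 4.1.1, the registration list in 4.2.2, the criteria in 4.2.3, the drug administration text in 4.3 and the remaining calendar notes do not mention a pre-dose pregnancy test. Section 7.1.3 requires an eligibility checklist at registration. Registration must precede treatment (4.2.2) but may be days earlier, so the checklist can be completed before the 24-hour window opens.

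**The case against.** The best reply is that nothing in the calendar overrides 3.1.9. It is a mandatory criterion, the calendar does not forbid an extra test, and a Day -29 test timed within 24 hours satisfies everything. Pregnant women are excluded (3.2.8) and contraception is required. This stands, and it is why the point concerns a possible breach and why the residual risk is limited.

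A second reply is that footnote a was meant only for labs with treatment thresholds in 4.2.3, and that a specific criterion should prevail over a general footnote. On precedence this is fair. On scope it is weak, because the footnote hangs on the Screening column header rather than on particular rows, and the pregnancy test is one of the laboratory tests in that column. The blank Day -28 cell remains a gap on either reading.

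Third, the contrast with the blood count and chemistry rows is softer than it looks. Their Day -28 marks carry asterisks, and a note with one more asterisk, probably meant for them, allows Days -42 through -28. That contrast should carry little weight, and the conclusion does not need it.

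Fourth, counting calendar days does not estimate how often a late test would occur. That is correct: the count shows what the schedule permits.

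Finally, one footnote might be enough. It would close the calendar gap, but footnote a would still read as permission to use an older result.

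**Conclusion.** The concern holds. The calendar and footnote a, as written, allow a pregnancy test older than Section 3.1.9 accepts, and no pre-dose check in the protocol is sure to catch it. With infusion on Day -28, 13 of the 14 screening days cannot meet the 24-hour limit. If footnote a covers this test and means up to three days before dosing, two of the three days it leaves usable also fail. The blank Day -28 cell does not depend on how footnote a is read.

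The consequence is a possible eligibility deviation with a possible fetal exposure. Sample size, stopping rules and analyses are unaffected. The protocol does not say how many women of childbearing potential are expected; total enrolment is up to 26. The inconsistency should be corrected because it concerns participant safety and the correction is simple.

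**What to change.** 1. In Section 4.10, mark the Day -28 cell of the pregnancy test row and add a footnote: *for women of childbearing potential, a negative result is required within 24 hours before infusion.* Worded this way, a Day -29 test inside that limit serves for both the Screening and Day -28 marks.
2. Add to footnote a: *this does not apply to the pregnancy test.*
3. Add a row to the table in Section 4.2.3: *pregnancy test (women of childbearing potential only): negative urine or serum result, with the sensitivity given in 3.1.9, within 24 hours before infusion.*

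The longest gap the schedule allows between test and dose then falls from 14 days (or 3 days under footnote a) to 24 hours. The cost is one calendar mark, one footnote, one sentence and one table row. No procedure is added beyond what 3.1.9 already requires.

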3.2 Exclusion Criteria

- 3.2.1 Any active history of a known autoimmune disease. Subjects with vitiligo, type 1 diabetes mellitus, residual hypothyroidism requiring hormone replacement, or conditions not expected to recur in the absence of an external trigger are permitted to enroll.
- 3.2.2 Patients who have had prior chemotherapy for newly diagnosed (cohort 1) or recurrent (cohort 2) head and neck cancer. In cohort 2 only, previous perioperative chemotherapy or chemoradiation for the management of localized or locally advanced disease is permitted.
- 3.2.3 Patients who received prior therapy with anti-PD-1, anti-PD-L1, anti-PD-L2, anti CD137, anti-CTLA-4 antibody therapies, any other antibody or drug specifically

targeting T-cell co-stimulation or checkpoint pathways.

- 3.2.4 Any live / attenuated vaccine (e.g. varicella, zoster, yellow fever, rotavirus, oral polio and measles, mumps, rubella (MMR) etc.) within 30 days of first treatment.
- 3.2.5 Patients with uncontrolled brain metastases

Patients with brain metastases must have stable neurologic status following local therapy (surgery and/or radiation) for at least 2 weeks without the use of steroids or on stable or decreasing dose of ≤ 10 mg daily prednisone (or equivalent), and must be without neurologic dysfunction that would confound the evaluation of neurologic and other adverse events. Patients with a history of carcinomatous meningitis are not eligible.
- 3.2.6 Patients who have an active concurrent malignancy that is not controlled/cured and could impact life expectancy within the next 3 years. E.g. patients with localized cutaneous squamous cell carcinoma or basal cell carcinoma or treated prostate cancer with no evidence of disease progression may be allowed to enroll after review by the study team and principal investigator.
- 3.2.7 Uncontrolled inter-current illness including, but not limited to, ongoing or active infection, symptomatic congestive heart failure, unstable angina pectoris, uncontrolled cardiac arrhythmia, myocardial infarction or new onset angina within six months of enrollment, or psychiatric illness/social situations that would limit compliance with study requirements.
- 3.2.8 Women who are pregnant or nursing.
- 3.2.9 Men with female partners who are not willing to use contraception.
- 3.2.10 Active infection with hepatitis B or hepatitis C (active infection is defined by abnormal liver function tests (=elevated AST/ALT) or ongoing use of an antiviral hepatitis treatment). Patients with **normal liver function tests** (defined by normal AST/ALT) per definition do not have an active infection and are eligible to enroll without additional testing).
- 3.2.11 Patients with a condition requiring systemic treatment with either corticosteroids (>10 mg daily prednisone equivalent) or other immunosuppressive medications within 14 days of randomization. However, inhaled or topical steroids and adrenal replacement steroid doses ≤ 10 mg daily prednisone equivalent, are permitted in the absence of active autoimmune

disease.

3.2.12 EBV(+) head and neck cancer (e.g. EBV(+) nasopharyngeal carcinoma)

3.2.13 Patient with HIV are excluded given the unknown risk of interaction with HAART and the unknown benefit of immunotherapy in this population.

3.3 Inclusion of Women and Minorities

Both men and women of all races and ethnic groups are eligible for this trial.

4. TREATMENT PLAN

4.1 Overall Study Design and Toxicity Assessment

The study will accrue to 2 cohorts, each of which consists of 12 patients who undergo surgical resection. Total of 26 patients will be accrued to the study. Patients who do not undergo surgery for reasons unrelated to toxicity of the study treatment will be replaced and will not count toward the accrual goal of 12 surgically resected patients in each cohort. If enrollment on 1 cohort is significantly faster, the lesser enrolling cohort number of patients may be decreased in favor of the better enrolling cohort to keep the total number of evaluable patients at 26 pts (also see statistical section).

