10.2 Sample Size, Analysis, and Accrual Rate

This study is investigating the safety and feasibility of neoadjuvant nivolumab administration in patients with locoregional newly diagnosed, recurrent or oligometastatic disease undergoing surgical resection. The study will enroll patients in two cohorts with an expected 12 patients in each cohort (although exact allocation may vary), who will undergo surgery in each cohort; the total sample size will be up to 26 patients. Subjects who sign a consent form but do not initiate protocol treatment for any reason (e.g., subjects who are screen failures), and patients who do not undergo surgical resection (for reasons unrelated to the study drug or toxicity) will be replaced and will not count towards our accrual goal.

The goal for the primary analysis of safety is to estimate the rate of DLTs (as defined in section 5.1) (AEs). We will provide the proportion of patients experiencing AEs, along with 95% confidence interval. Based on our study of neoadjuvant nivolumab in resectable lung cancer, we assume that at most 5% of patients will develop drug-related AEs of grade 3 or higher. The estimate and corresponding two-sided 95% confidence interval (CI) for each cohort is listed in the table below and may be updated if allocation between cohorts is not balanced:

| Observed number of patients with grade 3 or higher toxicity | Observed rate | 95% CI (Clopper-Pearson) |
|---|---------------|--------------------------|
| 0 | 0 | 0% - 26.5% |
| 1 | 8.3% | 0.2% - 38.5% |
| 2 | 16.7% | 2.1% - 48.4% |

For feasibility, the estimate of percent patient proceeding to surgery without any extended treatment related delays and the corresponding 95% CI based on 11-12 patients is, but may be updated if allocation between cohorts varies further:

| Observed number of patients proceeding to surgery without extended delay | Observed rate | 95% CI (Clopper-Pearson) |
|--|---------------|--------------------------|
| 12 | 100% | 73.5% - 100% |
| 11 | 91.7% | 61.5% - 99.8% |

However, cohort size (e.g. in the case of imbalanced enrollment) may be split 13/11, or 14/10, after consultation with the study statistician.

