| In this many patients | 2-4 | 5-8 | 9-11 | 12 |

Operating characteristics of the safety stopping rule are shown below and are based on 5,000 simulations:

| Risk of AE | 0.15 | 0.20 | 0.25 | 0.30 | 0.35 | 0.40 |
|-----------------------|-------|------|-------|-------|------|-------|
| % of Time study stops | 16.7% | 30% | 42.2% | 55.4% | 69% | 78.7% |
| Expected sample size | 10.8 | 10 | 9.1 | 8.2 | 7.1 | 6.3 |

Feasibility stopping guideline: We will temporarily halt the accrual if the risk of delayed surgery due to neoadjuvant nivolumab appears to be higher than 25%. We use a stopping rule based on a Beta prior distribution with parameters 0.1 and 0.9. With this prior, there is 90% probability that this risk of high-grade toxicity is between 0 and 65%. If, given the data from patients already treated, the probability is at least 70% that the risk is greater than 25%, we will consider stopping accrual pending feasibility evaluation. Starting from the 2nd patients, the stopping rules are shown in Table 2.

Table 2. Stopping rule for feasibility.

| Number of patients whose surgery is delayed for >28 days | 2 | 3 | 4 | 5 |
|--|-----|-----|------|----|
| Out of this many patients | 2-4 | 5-8 | 9-11 | 12 |

Operating characteristics of the feasibility stopping rule are shown below and are based on 5,000 simulations:

| Risk of delayed surgery | 0.15 | 0.20 | 0.25 | 0.30 | 0.35 | 0.40 |
|-------------------------|-------|-------|-------|-------|-------|-------|
| % of Time study stops | 17.3% | 29.3% | 43.1% | 56.2% | 68.3% | 79.2% |
| Expected sample size | 10.8 | 10 | 9 | 8.1 | 7.1 | 6.2 |

We will report the proportion of patients experiencing high-grade toxicity with exact binomial 95% confidence intervals. The safety analysis population includes patients who receive one dose of nivolumab. We will also describe patient experiences with respect to feasibility as defined above. The analysis population for feasibility includes patients who receive one dose of nivolumab. All other adverse events will be similarly summarized by type and grade. Analyses of immune markers will be descriptive and/or graphical in nature.

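### The sample size is stated as 26, but the cohort sizes and permitted splits add up to 24, and the stopping tables end at patient 12 although the plan allows larger cohorts

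*Combined protocol and SAP*

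**What the plan says.** **Total.** The Summary enrols 26. Section 4.1 says "Total of 26 patients will be accrued to the study" and allows reallocation between cohorts "to keep the total number of evaluable patients at 26 pts", pointing to the statistical section. Section 4.2.2 says that "patients who do not undergo surgical resection will be replaced and will not count towards our accrual goal of 26 patients", with allocation ideally 1:1. Section 10.2 gives a total of up to 26 and bases its accrual time on a 26-patient study.

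**Cohort size.** Section 4.1 describes two cohorts, "each of which consists of 12 patients who undergo surgical resection". Section 10.2 plans for two cohorts "with an expected 12 patients in each cohort (although exact allocation may vary"), all going to surgery, and says that an imbalanced enrolment "may be split 13/11, or 14/10, after consultation with the study statistician".

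**Replacement and populations.** The Summary, 4.1, 4.8 and 10.2 replace patients who miss surgery for reasons unrelated to drug or toxicity. Section 4.2.2 has no such qualifier. Sections 4.2.2, 4.8 and 10.2 keep every dosed patient in the safety and feasibility assessment.

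**Statistics.** The interval tables in 10.2 use 12 patients and may be updated if allocation varies. The row labelled "In this many patients" in Table 1, and its counterpart in Table 2, run 2-4, 5-8, 9-11 and 12, with boundaries of 2, 3, 4 and 5. The rule behind both tables is a posterior probability of at least 0.70 that the risk exceeds 25%, with a Beta(1,3) prior for safety and a Beta(0.1,0.9) prior for feasibility.

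**The concern.** Within 4.1, two cohorts of 12 resected patients make 24, while the evaluable total is put at 26. The statistical section that 4.1 points to does not settle this, because each split it permits also makes 24. The replacement rule shows the same conflict: in 4.1 it protects a goal of 12 resected patients per cohort, and in 4.2.2 a goal of 26.

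Safety and feasibility are the primary endpoint, and the interval widths are the only justification given for the sample size. From the text, staff cannot tell whether accrual closes at 24 or 26 resected patients, or at 26 dosed. The monitoring tables also end at patient 12, while the plan allows a cohort to reach 13 or 14, and dosed patients who are replaced can take the number monitored higher under any target.

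**Working it through.** **1. The sums.**
- Cohort target (4.1, 10.2): 12 + 12 = 24.
- Permitted splits (10.2): 13 + 11 = 24 and 14 + 10 = 24.
- Stated total (Summary, 4.1, 4.2.2, 10.2): 26. A 1:1 allocation of 26 is 13/13, a size that 10.2 does not list.
- Difference: 2 patients. No section describes an allowance of two.

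**2. Printed intervals.** For 0 events in n, the two-sided 95% Clopper-Pearson upper limit is 1 − 0.025^(1/n). At n = 12 this is 26.5%, as printed. The other four printed intervals (1/12, 2/12, 11/12 and 12/12) also reproduce. At the other sizes in play:

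| n | Upper limit, 0 events |
|---|---|
| 10 | 30.8% |
| 11 | 28.5% |
| 12 | 26.5% |
| 13 | 24.7% |
| 14 | 23.2% |

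At n = 13, 1 event gives 7.7% (0.2% to 36.0%) and 2 events give 15.4% (1.9% to 45.4%). For feasibility, 13/13 has a lower limit of 75.3%, and 12/13 gives 92.3% (64.0% to 99.8%).

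**3. Printed boundaries.** The boundary at n is the smallest s with P(risk > 0.25) ≥ 0.70 under Beta(a + s, b + n − s). Looking from patient 2 onward, both priors return exactly the printed 2, 3, 4 and 5 for 2-4, 5-8, 9-11 and 12 patients. The same rule continued beyond 12:

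| n | s | Posterior, Beta(1,3) | Posterior, Beta(0.1,0.9) | Halt? |
|---|---|---|---|---|
| 12 | 4 | 0.687 | 0.672 | no |
| 12 | 5 | 0.852 | 0.857 | yes |
| 13 | 4 | 0.630 | 0.608 | no |
| 13 | 5 | 0.810 | 0.810 | yes |
| 14 | 5 | 0.765 | 0.760 | yes |
| 15 | 5 | 0.718 | 0.706 | yes |
| 16 | 5 | 0.668 | 0.651 | no |
| 16 | 6 | 0.825 | 0.825 | yes |
| 18 | 6 | 0.744 | 0.735 | yes |

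The boundary is therefore 5 for 12-15 patients and 6 for 16-18, under both priors.

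**4. Operating characteristics.** Exact halt probabilities, by forward recursion over the binomial path with a look after every patient from the second:

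| True risk | 0.15 | 0.20 | 0.25 | 0.30 | 0.35 | 0.40 |
|---|---|---|---|---|---|---|
| Printed, safety | 16.7% | 30% | 42.2% | 55.4% | 69% | 78.7% |
| Printed, feasibility | 17.3% | 29.3% | 43.1% | 56.2% | 68.3% | 79.2% |
| Exact, n = 12 | 16.9% | 29.3% | 43.1% | 56.7% | 69.1% | 79.3% |
| Exact, n = 13 | 17.1% | 29.8% | 44.0% | 58.0% | 70.6% | 80.9% |
| Exact, n = 14 | 17.5% | 30.7% | 45.6% | 60.3% | 73.1% | 83.2% |

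The printed rows agree with the exact n = 12 values to within 1.3 points (56.7 − 55.4), so they describe 12 per cohort. At 13 the halt probability rises by at most 1.6 points (80.9 − 79.3). At 14 it rises by at most 4.0 points (73.1 − 69.1), and by 2.5 points at a risk of 25% (45.6 − 43.1).

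**The case against.** The best defence is that 26 and 24 count different people. The 12 per cohort are resected patients, whereas 4.8 makes unresected patients evaluable for safety and feasibility. Under most of the replacement clauses, a patient who misses surgery because of toxicity is not replaced and so still counts. Twenty-four resected among up to 26 counted is then arithmetically possible, and 10.2 does say up to 26. This reading is available, but it is nowhere stated. Section 4.2.2 leaves all unresected patients out of the 26 whatever the reason, and the Summary, 4.1 and 4.2.2 use 26 as the number to be reached, not as a ceiling. The defence shows that the total is undefined; it does not reconcile the sections.

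Three further points stand in the plan's favour. First, a reader might infer that patients 13 and 14 in a cohort would be treated with no stated safety or feasibility boundary. The documents do not support that: 10.2 gives the prior, the 25% threshold and the 0.70 cut-off, and says that monitoring is continual. The tables only tabulate that rule, and its value at 13 and 14 equals the last printed entry. Second, a reader might infer that the printed boundaries are wrong for a 26-patient study. They are not, because they depend on the patient number within a cohort and not on the study total. Third, 10.2 already allows both interval tables to be updated if allocation varies and requires consultation with the study statistician for the uneven splits. No such wording accompanies the stopping tables or their operating characteristics.

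**Conclusion.** The inconsistency is real and worth correcting: the plan states 26, while every cohort size and split it gives adds up to 24. The gap is 2 patients, or 8% of 24 (2/24 = 8.3%). The intervals, boundaries and operating characteristics are correct for 12 per cohort and incomplete beyond that.

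The numerical effect is small. Moving from 12 to 13 per cohort lowers the zero-event upper limit by 1.8 points (26.5 − 24.7) and raises the halt probability at 25% risk by 0.9 points (44.0 − 43.1). That equals the difference between the two printed simulation rows at that risk (43.1 − 42.2), which share the same boundaries. The largest change in precision is in the smaller arm of a 14/10 split, where the zero-event upper limit is 30.8%; the plan already allows that interval to be updated. No power or type I error claim depends on the choice, since the aim is estimation.

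The figures assume that the rule is applied within each cohort after every patient from the second, that outcomes are known before the next look, and that a halt ends the path. The plan calls the halt temporary, so accrual could resume.

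**What to change.** 1. State one total in the Summary, 4.1, 4.2.2 and 10.2, and say whether it counts dosed or resected patients. Define evaluable in the same place, and word the replacement rule identically in all of these sections and in 4.8.
2. Make the cohort sizes and splits add up to that total. Either use 24, as 12/12, 13/11 or 14/10, or use 26, as 13/13 with splits that sum to 26. If 26 is chosen, restate the interval tables for n = 13 (0 events: 0% to 24.7%).
3. Extend Tables 1 and 2 past 12, counting dosed patients, from the plan's own priors and cut-off: 5 events in 12-15 patients and 6 in 16-18. The extension should also cover dosed patients who are later replaced.
4. Restate the operating characteristics for the largest permitted cohort, using the n = 13 or n = 14 rows above or the values for whatever maximum is set.

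The cost is wording and table edits. Choosing 24 resected adds no patients. Choosing 26 resected raises the resected target from 12 to 13 per cohort, which stays within the stated total of 26 if that total counts resected patients.
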